## **6 STUDY SUBJECTS**

### **6.1 Number of Subjects**

Approximately 3000 HCW, FR, and DDOT bus drivers, age 18 to 75 years, without symptoms of respiratory tract infections and without a history of testing positive for SARS-CoV-2 will be prospectively enrolled and randomized at Henry Ford Health System, Detroit COVID Consortium or the Detroit Public Health Building. The fourth non-randomized comparator arm will include Participants on chronic maintenance therapy with weight-based HCQ twice a day dosing for their autoimmune disease, which will be continued throughout the study. Enrollment in this group will be open as it will be a non-randomized treatment arm, with total numbers of HCW enrolled will be expected to be lower than the randomized groups. The total study duration is expected to be up to 2 years, with Participant enrollment targeted to begin in April 2020.

Randomization Schema will be generated by the Biostatistician at Department of Public Health Sciences (PHS) at HFHS prior to the study enrollment. Randomization will be stratified by study site and level of risk of exposure in two levels. High risk includes healthcare personnel working in either hospital or nursing home settings (including environmental service) who

work in COVID-19 care areas, emergency rooms and intensive care units caring for COVID-19 patients, nursing home HCW providing any direct patient care, first responders (FR) and DDOT bus drivers. Low risk group will include healthcare and supportive personnel who work in non-COVID-19 care areas, without direct patient contact, and those involved in administrative roles. All physicians and clinical staff who are involved in the patient's enrollment and follow-ups will be blinded to the study treatments. Once enrolled, each Participant will be assigned a unique identifier. This number, along with the assigned site number, will constitute the Subject ID. This process is defined by using the following format:

□□□ - □□□□□  
Site #    Subject #

Site # = 3-digit code for the site assigned by the investigators

Subject # = 5-digit sequential number assigned by site personnel/investigators

All subject-specific material (i.e., case report log and samples) must be labeled in accordance with this ID.

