## **8.3 Statistical Analyses and Sample Size**

The ITT will be used for testing the treatment efficacy based on patients who are SARS-CoVID-2 viremia negative at the baseline. The primary analysis will be to compare the rate of COVID-19 disease for each treatment group to the placebo group with a Mantel-Haenszel chi-square test with multiplicity adjustment using the Dunnett's step up method(11,12). The stratifying

variables will be those used for the randomization, site and High vs. Low risk groups. The high risk group include healthcare personnel (including environmental service) who work in COVID-19 care areas, emergency rooms and intensive care units caring for COVID-19 patients. First responders and DDOT bus drivers will be included as a high risk group. Low risk groups will include healthcare workers who work in non-COVID-19 care areas, without direct patient contact and those involved in administrative roles.

The DSMB chair will be provided with a weekly site SAE report to monitor safety. An interim analysis will be done when a half of patients have completed the 8 weeks assessments for an early treatment efficacy or a possible reassessment of study sample-size if the estimation of placebo rate is inadequate. Depending on response to the study intervention, the DSMB may decide it is necessary to stop/continue the trial if 1) there are safety concerns at any point in the trial or 2) there is evidence of treatment efficacy at the interim analysis; or recommendation for trial modification as it may be suggested, or 3) to continue the trial as designed. The DSMB will only stop the clinical trial for safety reasons.

Secondary analyses will be performed to evaluate the comparisons between the randomized arms and the chronic HCQ treatment comparator arm. Additional analyses will include assessments of inflammatory markers in both plasma and leukocytes, clinical characteristics associated with risk for COVID-19 acquisition, disease specific markers and clinical symptoms, as well as virologic markers and sequencing of positive COVID-19 patients during the study. Safety and AE reporting will also be done as part of the study. A detailed statistical analysis plan (SAP) will be written before the study is closed.

Sample size/power calculation:

With one planned interim analysis when 50% of the participants have completed their 8 week treatment and using an O'Brien-Fleming alpha spending method to ensure an overall type 1

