6.1 Study Design

Participants who meet study entry criteria and are not on HCQ prior to study enrollment will be randomized in a 1:1:1 blinded comparison of daily or weekly hydroxychloroquine versus placebo for 8 weeks. The randomization will be stratified by enrolling site and high- vs. low- risk category, where the high-risk category will consist of HCWs who work in COVID-19 care areas.

A fourth non-randomized comparator group comprised of study participants who are already currently on standard HCQ therapy for an autoimmune disease(s) will be used to assess the impact of weight-based daily dosing of HCQ as compared to the randomized arms.

The trial will use a pragmatic, adaptive enrichment design, in which the primary efficacy analysis will be based on all randomized patients with a negative screen for COVID-19 at baseline, whereas the safety analysis will be based on all randomized patients, including those who are later determined to have been positive for COVID-19 at baseline (given that there may be a time lag to get initial screening COVID-19 test results back after study enrollment).

The trial is designed to have one interim look—when 50% of subjects have completed the study and primary endpoint assessment—for an early treatment efficacy assessment, and possible reassessment of study sample-size if the estimation of placebo infection rate is inadequate.

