6.3.4. Proposed Analysis

6.3.4.1 General Statistical Consideration:

The statistical software package SAS® Version 9.4 or higher (SAS Institute, Cary, NC, USA) will be used to perform all analyses and to summarize data.

The analyses described in this statistical analysis plan (SAP) are considered a priori, in that they have been defined prior to database lock. Any analyses not described herein performed subsequent to database lock will be considered post hoc and exploratory.

6.3.4.2. Handling of missing data:

For summary statistics, results will be reported based upon observed data. The study will make all possible efforts to obtain patient's follow-up data and laboratory confirmation of infection for COVID 19 disease determination. The efficacy analysis will be performed based on all observed data assuming missing as random (MAR), two selected imputation approaches are specified for the sensitivity analysis.

6.3.4.3 Primary Efficacy Analysis.

The FAS is considered. Chi-square test will be used to compare the rate of COVID-19 disease in each randomized treatment group to that of the placebo group using Dunnett's step-up method to adjust for multiple comparisons and controlling for type I error^{1,2}. Specifically, Dunnett's step-up method uses a closed gatekeeping strategy, in which the largest p value will be evaluated first at critical value of 0.05; if that fails, the second p value will be evaluated at critical value of 0.0262 (details in the sample size /power calculation section). A treatment efficacy is detected if the largest p value <0.05 or the second p value <0.0262 . The results of

efficacy analysis will be validated through two specified imputation approaches described in below

Sensitivity Analysis #1: A Tipping Point Analysis (TPA) with delta-adjusting imputation

The primary analyses for COVID 19 disease is based on the observed data and the results are valid if the missing data are missing at random (MAR), meaning that the probability of a value being missing, conditional on the observed data and factors in the statistical model, is random and not dependent on the unknown value of the missing data point.

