Based on an $\alpha=0.05$ two-sided test, chi-square test/logistic regression with odds ratio estimates, and Haybittle-Peto alpha spending method to ensure an overall type I error, the critical value for the interim analysis will be 0.001 and the critical value for the final analysis will be 0.05. For data illustration, we have also included an O'Brien-Fleming spending function approach for controlling type I error with a critical value of 0.0054 for the interim analysis and 0.0492 for the final analysis.

Power calculations are based on $n=900$ or 935 participants per study arm, using a simulation approach ($n=10,000$ simulations) in three correction methods: #1 comparing the weekly and daily HCQ dose arms to the placebo group separately using the Dunnett's step-up approach; #2 comparing the weekly and daily HCQ dose arms to placebo separately using a conservative Bonferroni approach with critical value of 0.025 for each test at the final look; #3 comparing the combined weekly and daily HCQ dose arms to the placebo using a single test.

With Haybittle-Peto boundary and $\alpha=0.05$ at the final look, the Dunnett's step-up correction uses a closed gatekeeping strategy for testing the daily dose arm vs placebo and the weekly dose arm vs placebo separately: the largest p value tested first will be at 0.05; if that fails, the second test will be at p value 0.026, delivered from the last row of Table 2 of Dunnett and Tamhane (1992), and validated based on simulation using R *DunnettTests* package. Likewise, at the interim look, the largest p value tested first will be at 0.001; if that fails, the second test will be at 0.0005.

Table 1. Power for different scenarios using varying methods. Sample size was determined using the Dunnett's Step up method with the Haybittle-Peto boundary.

Haybittle-Peto approach	$p_0=0.1, p_1=0.073, p_2=0.063$		$p_0=0.1, p_1=p_2=0.068$	
Method	n=900	n=935	n=900	n=935
#1 Dunnett's Step up	0.800	0.811	0.770	0.800
#2 Bonferroni	0.784	0.800	0.745	0.760
#3 Daily+weekly arms vs placebo	0.812	0.83	0.819	0.835

p_0 is the rate for the placebo treated group and p_1 and p_2 are the rates for the two treated groups.

O'Brien-Fleming approach	$p_0=0.1, p_1=0.073, p_2=0.063$		$p_0=0.1, p_1=p_2=0.068$		
Method	n=910	n=935	n=900	n=935	n=970
#1 Dunnett's Step up	0.8	0.814	0.76	0.776	0.801
#2 Bonferroni	0.787	0.8	0.741	0.761	0.784
#3 Daily+weekly arms vs placebo	0.815	0.83	0.815	0.83	0.846

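### The protocol tests the primary endpoint with a Mantel-Haenszel test on the randomisation strata; the SAP names only a chi-square test, with no strata and no reason for the change

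*SAP*

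**What the plan says.** **Randomisation.** Protocol 6.1: "Randomization will be stratified by study site and level of risk of exposure in two levels". SAP 6.1 keeps this: "The randomization will be stratified by enrolling site and high- vs. low- risk category".

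**Primary test in the protocol.** Protocol 8.3 compares each HCQ arm with placebo "with a Mantel-Haenszel chi-square test with multiplicity adjustment" by the Dunnett step-up method. It adds that the stratifying "variables will be those used for the randomization, site and High vs. Low risk groups".

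**Primary test in the SAP.** SAP 6.3.4.3: "Chi-square test will be used to compare the rate of COVID-19 disease in each randomized treatment group to that of the placebo group", again with the step-up method (0.05, then 0.0262). The power section, SAP 6.4, uses a third wording: "chi-square test/logistic regression with odds ratio estimates". The SAP nowhere mentions Mantel-Haenszel or adjustment for the strata in the primary analysis.

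**Definition of high risk.** Protocol 6.1 includes "nursing home HCW providing any direct patient care, first responders (FR) and DDOT bus drivers" as well as staff in COVID-19 areas, emergency rooms and intensive care. In SAP 6.1, "the high-risk category will consist of HCWs who work in COVID-19 care areas".

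**The concern.** When randomisation is stratified, the natural primary test conditions on the strata, and the protocol says so. The SAP keeps the stratified randomisation but drops the stratified test without comment, although it does document its change of primary aim.

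Two things follow.

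- **It is unclear which test was prespecified.** SAP 6 presents the plan as covering statistical matters the protocol left open, but the protocol had already settled the primary test. SAP 6.3.4.1 treats any undescribed analysis done after database lock as post hoc. Read literally, that covers the protocol's own primary test. If the two p-values fall on opposite sides of 0.05 or 0.0262, no sentence says which one counts.
- **Ignoring prognostic strata costs some power.** The unstratified variance includes between-stratum variation that stratified allocation has already removed from the treatment comparison. The test is then conservative.

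The strata themselves are also not described consistently, which matters for any stratified analysis, primary or supportive.

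**Working it through.** **1. The passages side by side**

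| Item | Protocol 6.1 | Protocol 8.3 | SAP |
|---|---|---|---|
| Randomisation strata | site, two risk levels | same (by reference) | site, high/low risk (6.1) |
| Primary test | – | Mantel-Haenszel on those strata | chi-square (6.3.4.3); chi-square or logistic regression (6.4) |
| Nursing-home direct-care staff | high | not listed | not listed in 6.1 |
| First responders, bus drivers | high | high | not listed in 6.1 |
| Medical students, household members | not enrolled | not enrolled | enrolled (1.1), not placed |

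**2. The SAP's own power figures**

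Inputs from SAP 6.4: placebo 10%, both HCQ arms 6.8%, shared placebo arm, interim look at half the participants (0.001, then 0.0005), final look (0.05, then 0.0262 as in 6.3.4.3). Power means that at least one HCQ arm is declared effective. Simulation with the unstratified pooled two-proportion test gives:

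| Rates in the HCQ arms | n per arm | SAP Table 1 | Simulated |
|---|---|---|---|
| 6.8%, 6.8% | 900 | 0.770 | 0.765 |
| 6.8%, 6.8% | 935 | 0.800 | 0.781 |
| 7.3%, 6.3% | 900 | 0.800 | 0.800 |
| 7.3%, 6.3% | 935 | 0.811 | 0.816 |

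The SAP's table is therefore consistent with an unstratified test. This does not prove that one was used, because a stratified test with non-prognostic strata gives the same power.

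**3. Why the unstratified test is conservative**

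Let stratum s have share w_s and event rate p_s, with arms balanced within strata. Under the null:

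- true variance of the difference in rates: (2/n) Σ w_s p_s(1 − p_s)
- variance used by the unstratified test: (2/n) p̄(1 − p̄)
- ratio R = Σ w_s p_s(1 − p_s) / [p̄(1 − p̄)]

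With p̄ = 0.10 the denominator is 0.09. Shares and rate ratios are assumptions, scaled to an overall placebo rate of 10%:

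| High:low ratio, high-risk share | Stratum rates | R | Simulated variance of z |
|---|---|---|---|
| 2:1, 50% | 13.3%, 6.7% | 0.0889/0.09 = 0.988 | 0.987 |
| 3:1, 50% | 15%, 5% | 0.0875/0.09 = 0.972 | 0.970 |
| 9:1, 50% | 18%, 2% | 0.0836/0.09 = 0.929 | 0.931 |
| 9:1, 30% | 26.5%, 2.9% | 0.0784/0.09 = 0.871 | 0.870 |
| four equal strata | 23.5%, 11.8%, 3.9%, 0.8% | 0.0823/0.09 = 0.915 | 0.915 |

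R cannot exceed 1, so the error rate cannot rise. For a single comparison at 9:1 with equal shares, the actual level is 2[1 − Φ(1.96/√0.929)] = 2[1 − Φ(2.03)] = 0.042.

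**4. Effect on the full procedure**

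The Mantel-Haenszel statistic for one HCQ arm against placebo is z = Σ(x_s − E_s)/√ΣV_s, with V_s = n_0 n_1 t(N − t)/[N²(N − 1)] in each stratum, where t is the number of events and N = n_0 + n_1. Each scenario used 200,000 simulated trials, 935 per arm, an interim look at 467 per arm, the SAP's thresholds, and relative risk 1.0 (null) or 0.68 (alternative) in both HCQ arms.

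| High:low ratio | High-risk share | Family-wise error, unstratified | Power gain from stratifying (points) |
|---|---|---|---|
| 1:1 | any | 5.0% | 0 |
| 2:1 | 30 / 50 / 70 / 90% | 4.8 / 4.9 / 4.9 / 5.0% | 0.3 / 0.3 / 0.1 / 0.0 |
| 3:1 | 30 / 50 / 70 / 90% | 4.5 / 4.6 / 4.8 / 5.0% | 0.9 / 0.7 / 0.4 / 0.0 |
| 9:1 | 30 / 50 / 70 / 90% | 3.3 / 4.1 / 4.6 / 5.0% | 3.6 / 1.9 / 0.9 / 0.1 |
| four strata | – | 3.9% | 2.3 (78.8% to 81.1%) |

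Mantel-Haenszel error stays at about 5% throughout. The two tests reach different conclusions in 0 to 3.6% of trials under the alternative.

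A separate simulation (900 per arm, final look only) agrees. Power goes from 76.6% to 77.0% at 2:1, from 76.7% to 77.6% at 3:1, and from 76.8% to 78.9% at 9:1, all with equal shares. With ten site-by-risk strata it goes from 76.4% to 77.5%.

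**The case against.** The effect is small. Nothing here creates a false claim of benefit, and gains of 2 points or more need assumed risk gradients that the documents do not supply. This stands, and it is why the point is a recommended correction and not a threat to validity.

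The supplied protocol may not be the version behind this SAP. The SAP cites a protocol dated 05/26/2020, covers Michigan and Ohio, enrols groups the protocol does not list, mentions a revision to include pregnant women, and uses a Haybittle-Peto boundary where the protocol has O'Brien-Fleming. A later version may have changed both the test and the strata. This also stands as a limit: the finding is that neither supplied document gives a reason, not that none exists. It also explains why the supplied protocol does not place medical students or household members.

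The SAP is coherent in itself: its test matches its power section, and an unstratified comparison after stratified randomisation is valid. That is correct, but it does not resolve the conflict with the protocol.

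Secondary aim S8 already models the primary endpoint on work type, location and treatment. It is secondary and retains variables by p-value, so it cannot stand in for a prespecified stratified test.

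The mismatch in risk definitions matters less than it first appears, because protocol 8.3 ties the analysis to the strata used for randomisation. The recorded strata would govern, whatever the prose says. The omission of nursing-home staff in protocol 8.3 is still a mismatch within one document.

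**Conclusion.** The concern holds. The protocol specifies a stratified primary test, the SAP names a test without strata, and neither document says why. The unstratified test does not inflate type I error. Under assumed strata, its family-wise error is 4.5 to 5.0% for risk ratios up to 3:1 and falls to about 3.3% in the most extreme case examined. The power lost is 0 to 1 point at 2:1 to 3:1, about 2 points at 9:1 with equal shares, and 3 to 4 only in extreme cases. It is nil if the strata are not prognostic.

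These sizes assume balanced arms within strata, the same relative reduction in every stratum, and an overall placebo rate of 10%. The case for acting rests mainly on having one unambiguous primary test fixed before unblinding; the power gain is secondary.

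**What to change.** **Primary analysis (SAP 6.3.4.3).** Name the Mantel-Haenszel test stratified by site and risk group as recorded at randomisation. Keep the step-up thresholds, report the Mantel-Haenszel risk difference or odds ratio, and keep the unstratified chi-square as a sensitivity analysis. Align the wording in SAP 6.4. Prespecify a blinded rule for pooling small sites within risk group.

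**If the unstratified test was intended.** State the reason and add the stratified test as a sensitivity analysis.

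**Strata.** Use one definition of high risk in protocol 6.1, protocol 8.3 and SAP 6.1, and say where medical students and household members fall.

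**Imputation analyses (#1 and #2).** Include the strata in the imputation model. The imputed endpoint is not rounded to 0 or 1, so the usual Mantel-Haenszel test cannot be applied to it directly. A Mantel-Haenszel-weighted difference in stratum means per imputation, combined with PROC MIANALYZE, would match the primary analysis.

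**Cost.** A few SAP sentences and standard SAS output, with no new data and no change in sample size. The pooling rule is needed because SAP 1.4 allows more sites. Strata without events contribute nothing to the test.

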6.3.4.4 Secondary Aims, Hypotheses and Analyses

S1: To compare the rates of SARS-CoV 2 infection status between the randomized treatment arms and the control arms to determine the effect of HCQ dose in the prevention of COVID-19 viremia and disease.

Secondary Hypothesis (S1): There is a hydroxychloroquine dose effect on acquisition of SARS-CoV 2 infection status, compared to placebo.

The endpoint will be SARS-CoV 2 infection status, defined as 1) no SARS-CoV 2 test positive during study follow up; 2) SARS-CoV 2 test positive (i.e., at least one positive RT PCR, or both IgM and IgG positive serology) without clinical symptoms (“asymptomatic SARS-CoV 2 test positive”) 3) SARS-CoV 2 test positive with clinical symptoms (“symptomatic SARS-CoV 2 test positive”).

The analysis will be conducted using FAS. Ordinal logistic regression will be used and analysis will start testing the overall daily and weekly dose effect, followed by pairwise/subgroup comparisons if an overall dose effect is detected at 0.05 level.

S2: To compare the rates of SARS-CoV 2 infection status in the non-randomized comparator arm to the randomized groups to assess the impact of chronic weight-based dosing of HCQ for COVID-19 prevention.

Secondary Hypothesis (S2): There is weekly /daily HCQ dose effect on acquisition of SARS-CoV 2 infection, compared to patients who were already on HCQ.

The endpoint will be the same as described for S1. The analysis will include all randomized *in FAS and non-randomized study participants with at least one post-baseline follow-up.*

We will first test for treatment selection bias using the data collected at the baseline. Inverse probability treatment weighting (IPTW)/propensity score, or matched sub-cohort will be considered to adjust for imbalanced participant characteristics. A similar analysis to that of S1 will be used for testing hypothesis S2.

S3: To compare the rate of SARS-CoV 2 infections as measured by serum IgM/IgG in participants receiving HCQ versus placebo.

Secondary Hypothesis (S3): There is weekly /daily dose effect on status of SARS-CoV 2 infection as measured by serum IgM/IgG, compared to placebo.

The endpoint will be serum IgG/IgM status at each participant’s study conclusion, classified as:

1. Negative (consistently negative for both serologies)
2. Indeterminate (IgM positive, with IgG consistently negative)
3. Positive (IgM and IgG positive, or IgG positive)

The analysis will be conducted *using FAS*. Ordinal logistic regression will be used to study the status distribution differences among three Arms. Similar to the analysis for S1, the analysis will start testing the overall dose effect, followed by the pairwise comparison between each treated arm and placebo.

S4: To compare the seroprevalence of SARS-CoV 2 IgM/IgG positive samples at study entry and study conclusion in all participants receiving HCQ compared to those receiving placebo.

Secondary Hypothesis (S4): There is weekly /daily dose effect on change in SARS-CoV 2 seroprevalence at study conclusion from the baseline, compared to placebo.

Serum IgM/IgG status at baseline and at study conclusion will be classified into the three categories described for S3. **The endpoint** will be a change in serum IgM/IgG status (from negative at baseline to indeterminate or positive at study conclusion, or indeterminate at baseline to positive at study conclusion).

The analysis approach described for S1 will be used to study the dose effect on change in serum IgM/IgG status *based on all randomized subjects*.

S5: To compare the development of clinical symptoms or COVID-19 diagnosis in participants presenting asymptotically at study entry but identified as seropositive by serology at entry between the randomized treatment arms and comparator arm.

Secondary Hypothesis (S5): There is dose effect on development of clinical symptoms or COVID-19 diagnosis.

The endpoint will be the same as that defined for P1. This analysis will include all randomized study participants who, at baseline, have positive serology (IgM or IgG) but are clinically asymptomatic. The analysis approach described for S1 will be used for this analysis.

S6: To compare the clinical COVID-19 disease need for participants in each treatment arm to require emergency room visit, hospitalization, or ability to stay home without hospitalization.

Hypothesis (S6): There is dose effect on incidence of ED visit/hospitalization, compared to placebo.

The endpoint will be rate of COVID-related ED visits or hospitalizations (by end of the planned 8-week follow-up period, or within 30 days after SARS-CoV 2 test positive if the positive test occurs <30 days before the end of the planned 8-week follow-up period).

FAS will be considered. The analysis approach described for S1 will be used for this analysis.

S7: To determine the safety and tolerability of HCQ dosing for preventive strategy against COVID-19.

Secondary Hypothesis (S7): There is an HCQ dose effect on AEs and SAEs, compared to placebo.

The endpoint will be any AE and any SAE observed during the 8 weeks of follow-up after enrollment.

Safety Analysis Set is considered by including all randomized subjects.

A descriptive analysis will report AE frequency and grade distribution among the three arms, and include a detailed list of serious adverse events (SAEs).

S8: To examine other clinical determinants contributing to the risk of SARS-CoV 2 infection including demographics, work type and location, positive COVID-19 partners, possible exposures and clinical symptoms.

Secondary Hypothesis (S8): Risk for SARS-CoV 2 infection varies by subject demographics, work type and location, and clinical conditions.

The possible covariates will include subject demographics, work type and location, and clinical conditions at the baseline prior to study enrollment, as well as the study treatment status. The endpoint will be clinical COVID-19 disease confirmed by laboratory test (same endpoint as P1).

FAS is considered. Logit univariate and multivariate modeling will be conducted with consideration of possible treatment-by-baseline covariate interaction. Variables will be retained in the final model if there is significant individual effect or variable-by-treatment interaction at p-value 0.05. Area under the receiver operating characteristic curve (AUROC) will be used to assess the predictive ability.

S9: To examine the association between HCQ drug levels and development of COVID-19 symptoms or positive test results.

Secondary Hypothesis (S9): There is an association between HCQ drug levels and development of COVID-19 symptoms or positive test results.

The endpoint will be the same, as described for S1 *using FAS*.

A similar analysis as that described for S1 will be used. The analysis will include concentration of HCQ in blood at baseline, week 4 and week 8 as covariates.

S10: To identify immunologic, serological and inflammatory markers associated with acquisition and response to COVID-19 in both HCQ and placebo Participants developing laboratory or clinical confirmed disease.

Secondary Hypothesis (S10): There are immunologic, serological and inflammatory markers for COVID-19 positive.

Two separate endpoints, SARS-CoV 2 test positive, and COVID19 disease with SARS-CoV 2 test positive laboratory confirmation (P1), will be considered.

FAS is considered. The immunologic, serological and inflammatory markers will be collected using the baseline blood samples. The same analysis approach as described for S8 will be used for S10. The baseline variables identified from S8 will be included for S10 analysis.

